### **3.1.3 Screening Phase**

#### **3.1.3.1 Randomized Control Trial**

About 16% of the children seen at CHOP Primary Care Roxborough, 21% of those seen at CHOP Primary Care Indian Valley and 50% of those seen at CHOP Cobbs Creek have Medicaid. Children will be eligible to participate in this study if they were born  $\geq 35$  weeks estimated gestational age, without neurodevelopmental disabilities or congenital malformations, with Medicaid insurance (proxy measure for poverty), and at least 4 months of age at the time of enrollment. Children who are born premature  $< 35$  weeks EGA, who have neurodevelopmental disabilities, or who have congenital malformations are at increased risk of language delays and will be excluded. In addition, we will exclude families who do not speak English or Spanish, as the main measures of reading activity (StimQ, Appendix 5) and language development (Bayley Scales of Infant Development-III, Appendix 7) are only available in English and Spanish.

Potential subjects will be identified at the time of their four month well child visit using the electronic health record (EHR). The pediatrician or nurse overseeing the wellness visit will receive a notification to inquire whether the parent-child dyad would be interested in participating in the study. If the parent indicates interest, one of our research staff will be in contact to explain the study procedures, and arrange to meet with the parent-child dyad at a time before their 6 month wellness visit while the child is between 5 and 7 months of age. Research staff will obtain written informed consent from participants. Participants will be randomized to either the digital literacy arm or the standard literacy arm based on random assignment. Randomization sequences will be developed by the study team using computer-generated random numbers prior to study enrollment and will be placed in sealed opaque envelopes. Randomization will ensure equivalence between groups on measured and unmeasured characteristics and is considered to be the strongest protection against bias in study design.

Written informed consent will be obtained in person prior to any study related procedures being performed. The consenting process will include a discussion of study rationale, procedures, measures, benefits, risks, and alternatives to participation. After consent, subjects will either be assigned to the digital literacy arm or the standard literacy arm of the study. Regardless of their assignment, once they have consented to participate, they will complete a demographic questionnaire (Appendix 1), questionnaires about adverse childhood experiences (Appendix 2) and health literacy (Appendix 3), and the Edinburgh Postnatal Depression Scale (EPDS) (Appendix 4).

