### **3.1.4 Randomized Controlled Trial Treatment Phase (start of the study intervention)**

Once recruited and enrolled, the parent-child dyads will be randomized into either the digital or standard literacy arm. Parent-infant dyads randomized to the digital literacy arm will receive the digital e-book version of [name] *Hop on Pop* for the 6 month well visit, Sandra Boynton's *Barnyard Dance* for the 9 month well visit, and Margaret Wise' *Goodnight Moon* for the 12 month well visit. Moreover, they will receive information on the importance of early parent-child reading activity by pediatric clinicians. Information on early literacy will be standardized and age-based and will be provided to parents by pediatric clinicians at the well visits.

Parent-infant dyads randomized to the standard literacy arm will receive [name] *Hop on Pop* for the 6 month well visit, Sandra Boynton's *Barnyard Dance* for the 9 month well visit, and Margaret Wise' *Goodnight Moon* for the 12 month well visit. In addition, they will be provided information on the importance of parent-child reading activity by pediatric clinicians.

Information on early literacy will be standardized and age-based and will be provided to parents by pediatric clinicians at the well visits. This conforms to the ROR National Program recommendations and is considered standard of care at these 3 clinics.

To prevent contamination in which pediatric clinicians inadvertently provide books and instruction on reading activity to the different arms of the study, an automated alert will appear on the screen of the eligible child's EHR at each well visit with a reminder to the health professional. This will ensure that books and reading instructions are consistent with their assigned study arm. Phone call or text message reminders will be used throughout the course of the study. The initial reminder will be made within the first week to participants in the digital literacy arm to verify that the participant was able to download the e-book if this was not already confirmed during the initial visit. Another reminder will be sent out about 1 month after the infant has, or is age-eligible for, their 6, 9 and 12 month well visit, either to remind the participant to complete the emailed REDCap survey, or for other study-related reminders.

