Children in both study arms will be followed every 3 to 4 months until they are between 12 and 18 months, 30 days. Parents will complete study measures consisting of demographic characteristics, postpartum depression symptoms, health literacy, and adverse childhood experiences at the initial study visit. Parents will complete measures of reading activity at baseline, and via the REDCap survey sent by email, or completed in person, about 1 month after the infant has, or is age-eligible for, their 6, 9 and 12 month well visits. Differences in reading activities and language outcomes will be assessed between groups using intention-to-treat analysis.

Parents of children who are participating in the study will be informed of the results of their BSID-III testing in writing and/or by phone. Those whose child scores less than 1.5 standard deviations below the mean will be informed that their child's development is within the average range. Parents whose child scores 1.5 standard deviations or greater below the mean will be informed that their child is exhibiting delays in an area of their development. In addition, we will recommend that the parent inform their child's clinician of the results.

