## **4 STUDY PROCEDURES**

### **4.1 Screening/Consenting Visit and Study Visit 1**

- Identify eligible 4-month old infants at the time of their well child visit using the electronic health record (EHR)
- Recruit and consent eligible parent-child dyads at or before child's 6 month well visit.
- Randomize parent-child dyads into intervention and control groups.
- Collect baseline demographic, parent adversity, and parent mental health information.

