### 6.3 Statistical Methods

Summary statistics will be obtained, and differences between digital and standard arms will be assessed using intention-to-treat analysis. Cross-sectional differences in StimQ scores between digital and standard groups at the 6, 9 and 12 month well visits will be assessed using t-tests. To determine how the effects of digital versus standard literacy is associated with language development, we will develop regression models using longitudinal data methods that adjust for correlation in BSID-III scores over time and for potential confounding by demographic characteristics. To explore the impact of digital literacy on healthcare utilization, the EHR will be reviewed to identify a subjects' number of well visits and their vaccination history.

To determine whether parent adversity, health literacy, and/or parent mental health modify the effects of digital versus standard literacy on language development, we will develop similar regression models using longitudinal data methods, but we will also fit interaction terms between study group and ACE score ( $\geq 4$ ), SAHL (high or low) and EPDS score ( $> 10$ ). To determine if parent-child reading activity mediates the association of intervention group assignment and language development, we will use mediation analysis with separate models regressing group assignment on language development, parent-child reading activity on group assignment, and group assignment on language development adjusted for parent-child reading activity.

Assuming a mean cognitive subscale on the BSID-III of 96, a power of 0.70, an alpha of 0.05, and a clinically significant difference of 7.5 points on the BSID-III between groups, we estimate that we will need to recruit a total sample size of 100 eligible children (50 in each group) to participate in the main RCT study (Figure 1). To attain thematic saturation in the Video Sub-study, we will recruit up to 40 participants 9-12 months of age. These 40 participants may be recruited external to the main study if we are unable to recruit up to 40 from the 100 enrolled in the main study in a timely fashion. All analyses will be conducted using Stata Statistical Software, version 13 (College Station, TX).

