## **8.4 Recruitment Strategy**

### **8.4.1 Randomized Control Trial**

We will have an EHR recruitment prompt sent only to potentially eligible children with Medicaid at their 4 month well visit at the CHOP Primary Care Roxborough, PA, CHOP Primary Care Cobbs Creek and CHOP Primary Care Indian Valley. Parents who are conceivably interested in participating will be contacted by research staff. Research staff will briefly explain the study procedures, guided by the information set forth in the approved consent form. This includes reading the inclusion criteria to the potential participant, and asking whether or not this individual is interested in participating. Research staff will then schedule a time to meet with the parent in person. This will happen at a time before their infant's 6 month well visit in order to obtain informed consent, confirm that all of the inclusion criteria are met, and randomize the

participant into either the digital or standard book group. In the event that the research staff is unable to confirm that all inclusion criteria are met after the participant has been enrolled, the participant will no longer be able to participate. Additionally, potentially eligible 5 to 7 month olds that have been identified by study staff on EPIC as potentially eligible by screening via review of the medical record, may be approached in person before or at the time of their 6 month well visit. These potentially eligible participants will be screened, consented and enrolled into the study prior to the child's time with the provider.

We may also hang recruitment flyers in the hallways at both clinics giving information about the study and contact information for the study coordinator in case they are interested and we miss their names in the screening process.

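### Baseline forms are described after allocation, with no blinding described, so the baseline EPDS (and any baseline reading measure) can be influenced by knowledge of the arm

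*Combined protocol and SAP*

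**What the plan says.** **Order of steps.** Section 3.1.3.1 states: "After consent, subjects will either be assigned to the digital literacy arm or the standard literacy arm of the study". The next sentence reads: "Regardless of their assignment, once they have consented to participate, they will complete a demographic questionnaire", and goes on to the ACE, SAHL and EPDS forms. In section 4.1 the bullet "Randomize parent-child dyads into intervention and control groups" comes directly before "Collect baseline demographic, parent adversity, and parent mental health information". Section 8.4.1 describes the first meeting as the occasion to obtain consent, "confirm that all of the inclusion criteria are met, and randomize the" participant. It does not mention the questionnaires.

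**Knowledge of the arm.** Section 3.2 has blinding in its title but no text on it. Section 3.1.4 has a first-week reminder to verify that the "participant was able to download the e-book if this was not already confirmed during the initial visit".

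**Use in the analysis.** Section 6.3 adjusts the BSID-III model "for potential confounding by demographic characteristics". It also fits interactions of study group with ACE (≥4), SAHL (high or low) and EPDS (>10). Parent-child reading activity enters only as a mediator.

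**Reading at baseline.** Section 3.1.4 says: "Parents will complete measures of reading activity at baseline". The baseline lists in the Abstract (Study Interventions and Measures) and in sections 3.1.3.1 and 4.1 do not include it.

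**The concern.** A value recorded before allocation cannot depend on the arm. A value recorded after an unmasked allocation can, and if it then serves as a covariate or effect modifier, randomization no longer protects that part of the analysis. Two things are at stake.

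- **Reporting.** A parent who knows the arm may answer a symptom scale, or a question about reading, differently from a parent who does not.
- **Completeness.** A parent who stops on learning the arm has already been randomized and counts under intention to treat, but has no demographics, ACE, SAHL or EPDS. Section 6.3 gives no rule for missing data.

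BSID-III is measured only at the second study visit, so these forms are the main pre-intervention record of the dyads.

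**Working it through.** **1. Is the order consistent across the documents?** Sections 3.1.3.1 and 4.1 both give consent, allocation, questionnaires. Section 8.4.1 gives consent, eligibility, allocation. No section places the questionnaires before allocation or makes opening the envelope conditional on their completion.

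**2. Can a parent know the arm while answering?** Nothing conceals it. Section 3.1.4 allows the e-book download to be confirmed at the initial visit, and section 3.1.4 also places the baseline forms at that visit.

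**3. Which baseline values are used, and how exposed are they?**

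| Item | Use in section 6.3 | Exposure to knowledge of the arm |
|---|---|---|
| Demographics | Covariates | Low: largely fixed facts (age, sex, race/ethnicity, family structure, education, income category) |
| ACE (≥4) | Interaction | Low: past exposures |
| SAHL (high/low) | Interaction | Low: not described as self-report |
| EPDS (>10) | Interaction | Plausible: symptom scale cut at a threshold |
| Baseline reading | None | Plausible if collected, but not in any planned adjustment |

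**4. What follows for each analysis?**

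- *Unadjusted comparison.* The estimate is the difference in mean BSID-III between arms. It contains no baseline term, so this route cannot bias it.
- *Adjusted model.* Adjusted effect = (difference in mean BSID-III) − b × (difference in covariate means). Only an arm-driven part of the covariate difference causes bias. For the planned demographic covariates that part should be close to zero.
- *EPDS interaction.* Take no true arm effect. Let μH and μL be mean BSID-III for parents truly above 10 and truly at or below 10. Suppose the standard arm is classified correctly, and in the digital arm a share m of those recorded at or below 10 are truly above it and typical of that group.
  - Recorded ≤10: arm difference = [(1 − m)μL + mμH] − μL = m(μH − μL).
  - Recorded >10: arm difference = μH − μH = 0.
  - Spurious interaction = 0 − m(μH − μL) = m(μL − μH).

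  With the same m in both arms, both differences are zero. Only a difference in reporting between arms matters. The documents give neither m nor μL − μH, so no figure in points follows.

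**5. What would lost baseline data cost?** First, Figure 1 reproduces. Inputs are a 7.5-point difference (section 6.3), SD 15 (Figure 1) and alpha 0.05, taken as two-sided. Per arm, n = 2(z0.975 + zpower)²(15/7.5)² = 8(1.9600 + zpower)².

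- Power 0.70: 8 × 2.4844² = 49.38, so 50 per arm, 100 in total.
- Power 0.65: 8 × 2.3453² = 44.003, so 45 per arm, 90 in total.
- Power 0.60: 8 × 2.2133² = 39.19, so 40 per arm, 80 in total.

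All three rows agree with the plan. If an adjusted complete-case analysis dropped 10 of 100 dyads, planned power would fall from 0.70 to 0.65. Ten is a row of the plan's own table, not a forecast.

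**The case against.** The order is inferred, not laid down as a rule. Section 3.1.3.1 ties the forms to consent, and its reference to assignment can simply mean that both arms complete the same forms. The list in section 4.1 is unnumbered. No text says that a parent is told the arm before answering, and a download at the initial visit is compatible with disclosure at its end. Both arms receive the same titles and the same Reach Out and Read counselling, so part of any expectation effect would be shared. Nothing in the documents suggests that parents walk out, and section 8.6.1 pays $20 on completion of that visit.

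Most of this stands, and it limits the point. It does not remove it: two sections give the same sequence, none gives another, and a sequence left to inference can vary between staff and sites.

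A reader might also infer a bias in BSID-III points by multiplying the StimQ–Bayley correlation of 0.52 (section 5.1.4) by the SD of 15 and an assumed shift in reported baseline reading. The documents do not support that. Section 6.3 does not adjust for baseline reading, and it is unclear whether baseline reading is collected at all. The correlation is given for the StimQ, not specifically its Read subscale and not conditional on demographics. The shift would have to differ between arms, and no source for its size is given.

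**Conclusion.** The point holds as a modest and avoidable weakness in the order of procedures. As written, the baseline forms follow an unmasked allocation. The analysis mainly exposed is the EPDS (>10) by group interaction; baseline reading is exposed if it is collected. Loss of baseline data after allocation is possible, at the Figure 1 rate of 0.05 in power per ten dyads if the analysis is adjusted and complete-case. No bias in points can be stated.

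A reader might conclude that the randomized comparison itself is compromised. It is not: the unadjusted intention-to-treat contrast does not use these values, and the planned demographic adjustment rests on facts that the arm can hardly change.

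The conclusion assumes that staff follow the order as written, that at least some parents know the arm before they answer, that reporting differs between arms, and that section 6.3 means the baseline EPDS. Section 6.3 does not say which EPDS it uses, and section 7.2 has it collected twice.

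**What to change.** In sections 3.1.3.1 and 4.1, state one sequence: obtain consent, confirm eligibility, complete all baseline questionnaires, then open the envelope. Align section 8.4.1 with it.

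Reconcile section 3.1.4 with the Abstract and sections 3.1.3.1 and 4.1 on whether reading activity is measured at baseline. If it is, place it with the other forms before the envelope. In section 6.3, name the baseline EPDS as the modifier, if that is what is meant.

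The cost is essentially wording: the same visit, forms and staff. One practical detail needs planning. Section 8.4.1 allows dyads to be enrolled on the day of the 6-month visit before they see the clinician, so on those days the forms must be finished before the envelope is opened and the book is handed over.

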### **3.1.3.2 Video Sub-study**

Children will be eligible to participate in this sub-study if they were born  $\geq 35$  weeks estimated gestational age, without neurodevelopmental disabilities or congenital malformations, with Medicaid insurance (proxy measure for poverty), and, for participants being recruited externally, at least 9 months and 0 days and no more than 12 months and 0 days at the time of enrollment. As in the randomized control trial, children who are born premature  $< 35$  weeks EGA, who have neurodevelopmental disabilities, or who have congenital malformations will be excluded, as they are at increased risk of language delays. In addition, we will exclude families who do not speak English for this sub-study, as resources are not available in this pilot to execute and code video data in additional languages.

Potential subjects will be identified from 1) participants in the randomized control trial that previously consented to participate in the sub-study, were randomized into the control group (traditional board book arm), and are age-eligible for their 9 month well visit, and 2) eligible patients recruited from the Cobbs Creek clinic who are 9 to 12 months old. For participants recruited external to the randomized control trial, study staff will identify eligible participants and, when on-site at the time of the appointment, approach participants in person at the clinic before or after their appointment with the clinician. At that time, a member of our study staff will explain the study procedures and consent the parent and infant for participation. The consenting process will include a discussion of study rationale, procedures, measures, benefits, risks, and alternatives to participation. Once they have consented to participate, they will complete a demographic questionnaire (Appendix 1), questionnaires about adverse childhood experiences (Appendix 2) and health literacy (Appendix 3), and the Edinburgh Postnatal Depression Scale (EPDS) (Appendix 4). They will also schedule the parent and child for a study visit at that time if the parent is able. Parents who are unable to be scheduled for participation at that time will be contacted by study staff via telephone to schedule the study visit.

### **3.1.4 Randomized Controlled Trial Treatment Phase (start of the study intervention)**

Once recruited and enrolled, the parent-child dyads will be randomized into either the digital or standard literacy arm. Parent-infant dyads randomized to the digital literacy arm will receive the digital e-book version of [name] *Hop on Pop* for the 6 month well visit, Sandra Boynton's *Barnyard Dance* for the 9 month well visit, and Margaret Wise' *Goodnight Moon* for the 12 month well visit. Moreover, they will receive information on the importance of early parent-child reading activity by pediatric clinicians. Information on early literacy will be standardized and age-based and will be provided to parents by pediatric clinicians at the well visits.

Parent-infant dyads randomized to the standard literacy arm will receive [name] *Hop on Pop* for the 6 month well visit, Sandra Boynton's *Barnyard Dance* for the 9 month well visit, and Margaret Wise' *Goodnight Moon* for the 12 month well visit. In addition, they will be provided information on the importance of parent-child reading activity by pediatric clinicians.

Information on early literacy will be standardized and age-based and will be provided to parents by pediatric clinicians at the well visits. This conforms to the ROR National Program recommendations and is considered standard of care at these 3 clinics.

To prevent contamination in which pediatric clinicians inadvertently provide books and instruction on reading activity to the different arms of the study, an automated alert will appear on the screen of the eligible child's EHR at each well visit with a reminder to the health professional. This will ensure that books and reading instructions are consistent with their assigned study arm. Phone call or text message reminders will be used throughout the course of the study. The initial reminder will be made within the first week to participants in the digital literacy arm to verify that the participant was able to download the e-book if this was not already confirmed during the initial visit. Another reminder will be sent out about 1 month after the infant has, or is age-eligible for, their 6, 9 and 12 month well visit, either to remind the participant to complete the emailed REDCap survey, or for other study-related reminders.

Children in both study arms will be followed every 3 to 4 months until they are between 12 and 18 months, 30 days. Parents will complete study measures consisting of demographic characteristics, postpartum depression symptoms, health literacy, and adverse childhood experiences at the initial study visit. Parents will complete measures of reading activity at baseline, and via the REDCap survey sent by email, or completed in person, about 1 month after the infant has, or is age-eligible for, their 6, 9 and 12 month well visits. Differences in reading activities and language outcomes will be assessed between groups using intention-to-treat analysis.

Parents of children who are participating in the study will be informed of the results of their BSID-III testing in writing and/or by phone. Those whose child scores less than 1.5 standard deviations below the mean will be informed that their child's development is within the average range. Parents whose child scores 1.5 standard deviations or greater below the mean will be informed that their child is exhibiting delays in an area of their development. In addition, we will recommend that the parent inform their child's clinician of the results.

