#### Study Interventions and Measures:

In this intervention, parent-infant dyads randomized to the digital arm will receive developmentally appropriate e-books. Those randomized to the standard arm will receive developmentally appropriate board books. Participants will receive either the e-book or board book for their 6, 9 and 12 month well visits. The developmentally appropriate books selected for each of the 3 well visits are as follows: [name] *Hop on Pop* for the 6 month well visit, Sandra Boynton's *Barnyard Dance* for the 9 month well visit, and Margaret Wise' *Goodnight Moon* for the 12 month well visit.

In addition to the books, parent-infant dyads in both arms will be provided information on the importance of early parent-child reading activity by pediatric clinicians using the Reach Out and Read framework.

We will collect standard measures of demographics (child age, sex, race/ethnicity, maternal age, family structure, maternal education level, and family income category), maternal adversity (9 ACE questions), maternal health literacy (SAHL), and maternal depressive symptoms (EPDS) at baseline. About 1 month after the infant has, or is age-eligible for, their 6 and 9 month well visits we will collect measures of reading activity (StimQ and ERPQ). Roughly 1 month after the infant has, or is age eligible for, their 12 month well visit, the infant will receive a developmental assessment (BSID-III), along with additional measures of reading activity (StimQ, ERPQ). They will additionally complete the paper-based DialogPR-I at this visit. A video recorded reading task will be obtained for up to 40 participants. These participants will be asked preliminary questions about their reading practices at home at the time of the video session.

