Participants in both study arms will be followed every 3 to 4 months until the infants are between the ages of 12 and 18 months, 30 days. Information on reading activities and developmental outcomes will be collected in concert with scheduled well child visits. Differences in reading activities and developmental outcomes will be assessed between groups using intention-to-treat analysis. Parents will complete measures of demographics, health literacy, and maternal depressive symptoms at baseline. Parents will also complete measures of reading activity with their infant about 1 month after the child has, or is age-eligible for, their 6, 9, and 12 month well visits. The infant will also receive a developmental assessment at the second study visit which will happen about 1 month after they have, or are age-eligible for, their 12 month well visit. At this time the infant should be between 12 and 18 months, 30 days old. Secondary data to address these study questions does not exist, which will necessitate the collection of new data as proposed here. We anticipate that this collection of rich new data will support a careful assessment of the effects of digital vs. standard literacy promotion. The HER will be reviewed for children in both arms to count the number of well child visits and examine their vaccination history.

We anticipate collecting this data in conjunction with well child visits. In our experience, low-income families can be difficult to reach for study visits, even with appropriate study incentives. By coordinating data collection with the 6, 9, and 12 month well child visits timeframes, we can increase the probability of families attending both the well visits (to receive the Reach Out and Read Program materials) and the study visits (to collect measures of reading activity and development). In a previous study of 2100 children enrolled in a study of developmental screening, we were able to achieve a >90% follow-up rate by coordinating data collection with well child visits. In addition, our research staff can check the clinic schedule to ensure families have made timely well child visit appointments and then make reminder calls to families prior to these visits to encourage parents to attend. Study visits will be held at a location that is preferred

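### Baseline reading activity is promised in one sentence but absent from every list of baseline measures, and StimQ is then compared by three unadjusted t-tests with no lead comparison

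*Combined protocol and SAP*

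**What the plan says.** **Baseline.** Section 3.1.4 is the only place that puts reading measures at baseline: "Parents will complete measures of reading activity at baseline". The other descriptions of baseline leave them out:

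- The preceding sentence of 3.1.4 lists demographics together with "postpartum depression symptoms, health literacy, and adverse childhood experiences at the initial study visit".
- The abstract (Study Interventions and Measures) lists demographics and "maternal adversity (9 ACE questions), maternal health literacy (SAHL), and maternal depressive symptoms (EPDS) at baseline".
- Section 3.1.1: "Parents will complete measures of demographics, health literacy, and maternal depressive symptoms at baseline".
- Section 3.1.3.1 names the post-consent questionnaires by appendix, 1 to 4. The same section identifies StimQ as Appendix 5, which is not among them.
- Section 4.1: "Collect baseline demographic, parent adversity, and parent mental health information".

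**Follow-up.** The abstract and sections 3.1.1, 4.2 and 6.2 schedule reading measures about one month after the 6, 9 and 12 month visits.

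**Analysis.** Section 6.2 makes StimQ a secondary endpoint. Under 6.3, StimQ differences between arms "at the 6, 9 and 12 month well visits will be assessed using t-tests". No covariate, lead time point or multiplicity rule is given. The longitudinal, covariate-adjusted models in 6.3 are written for BSID-III, which section 6.1 places at a single visit. Clinic site is the stratification factor (3.2).

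**The concern.** The first scheduled StimQ comes about a month after the 6 month visit, when the first book and counselling are due. If StimQ is not completed at visit 1, no later measurement can stand in for a pre-intervention value.

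The planned analysis would not use such a value even if it were collected. It also leaves out the factor on which randomization is stratified, and it treats three correlated measurements on the same families as three unrelated comparisons. With none of the three named as the main one, a mixed set of results (one visit significant, two not) has no agreed reading.

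What is at stake is how precisely and how clearly the plan answers Aim 2, which concerns reading behaviour. The BSID-III comparison is not touched.

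**Working it through.** **1. The plan's own figure.** Inputs from 6.3 and Figure 1: BSID-III difference 7.5, SD 15, alpha 0.05, power 0.70. With a two-sided test, n per arm = 2 × (1.960 + 0.524)² × 15² / 7.5² = 49.4, rounded up to 50, so N = 100. At power 0.60 and 0.65 the same formula gives 39.2 and just over 44.0, rounded up to 40 and 45 per arm, so N = 80 and 90. All three rows of Figure 1 reproduce. The documents give no corresponding figure for StimQ.

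**2. Value of a baseline StimQ at one visit.** Assumptions: 50 per arm; a difference of 7.5/15 = 0.5 SD, carried over from BSID-III because the documents give no StimQ effect or SD; two-sided 0.05. Adjusting for a baseline with correlation r multiplies the residual variance by 1 − r², so the effective standardized difference is 0.5/√(1 − r²). Power is from the noncentral t distribution.

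| r (assumed) | 1 − r² | effective difference | power |
|---|---|---|---|
| unadjusted | 1.00 | 0.500 | 0.70 |
| 0.2 | 0.96 | 0.510 | 0.71 |
| 0.3 | 0.91 | 0.524 | 0.74 |
| 0.5 | 0.75 | 0.577 | 0.82 |
| 0.7 | 0.51 | 0.700 | 0.93 |

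The documents give no correlation between StimQ at 5 to 7 months and StimQ at follow-up. The test-retest value of 0.84 in 5.1.4 is at most a rough upper bound. At r = 0.5, 100 adjusted dyads carry the information of 100/0.75 = 133 unadjusted ones. At r = 0.2 the figure is 100/0.96 = 104, which is close to no gain.

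**3. Three tests.** Assume each is read at 0.05; the plan states that level only for the BSID-III sample size. If the tests were independent, the chance of at least one false positive would be 1 − 0.95³ = 14.3%. They are correlated, so the chance was simulated with 2 million draws from a trivariate normal with equal correlations: 13.6% at 0.3, 12.5% at 0.5, 10.9% at 0.7 and 9.3% at 0.84. The fair range is about 9% to 14%.

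**4. Which lead contrast.** Set every correlation, including that with baseline, to 0.5. The baseline-adjusted average of three visits then has variance factor (1 + 2 × 0.5)/3 − 0.5² = 0.417.

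- Constant 0.5 SD effect: 0.5/√0.417 = 0.775, power 0.97.
- Effect building up as 1/3, 2/3 and all of 0.5 SD: the mean effect is 0.333, 0.333/√0.417 = 0.516, power 0.72. The baseline-adjusted final-visit test has 0.82.

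The ranking reverses with the shape of the effect, which the documents do not state.

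**5. Without any baseline.** The average of three visits has variance factor (1 + 2ρ)/3. With a constant 0.5 SD effect and complete data, power is 0.92, 0.86 or 0.79 at between-visit correlation ρ = 0.3, 0.5 or 0.7, against 0.70 for one t-test. Under a constant effect, pooling the visits therefore helps even if baseline StimQ is not collected.

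**The case against.** - **A reader might infer that baseline StimQ will not be collected.** The documents do not prove this. The 4.1 list is not exhaustive: it also omits health literacy, which the other baseline lists include. Section 3.1.1 in turn omits parental adversity. The appendices are not visible, so the actual visit 1 packet is unknown. What stands is a contradiction that makes non-collection likely. Section 3.1.3.1 itemizes the questionnaires by appendix without StimQ, and 4.2 names StimQ and ERPQ outright where it wants them, as for externally recruited video families.
- **A reader might infer that the t-tests are biased or invalid, or that the trial's error rate is inflated.** Neither follows. Randomization balances prior reading habits in expectation, each test keeps its own level, and the BSID-III error rate is unaffected. StimQ is secondary and Aim 2 is worded as exploratory, so the family-wise figure describes how the results might be misread. It does not show that a stated error rate is breached.
- **A reader might infer large pre-existing differences between families.** The documents give no figure for this. The 0.5 SD effect and the correlations are also assumptions, and at r = 0.2 the gain from adjustment is negligible. This objection stands in full, and the power figures are illustrative only.
- **A reader might infer that the average arm effect should be the lead test.** Books accumulate one per visit, so the effect may grow, and a final-visit test could then do better. The choice is a trade-off.

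Deleting the baseline clause would also remove the contradiction, but it would give up the precision that a baseline offers.

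**Conclusion.** The point holds at moderate weight. The contradiction over baseline reading measures is plain in the text and should be resolved, because a missed pre-intervention value cannot be recovered. The StimQ analysis is valid but inefficient: it uses neither baseline nor site, and it leaves three correlated results without a lead.

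On the stated assumptions (50 per arm, 0.5 SD borrowed from BSID-III, one visit), power rises from 0.70 to between 0.71 and 0.93 for correlations of 0.2 to 0.7. If 0.05 is applied to each of the three tests, the chance of some false positive is about 9% to 14%. The loss is in precision and interpretability of a secondary outcome; the primary comparison and the sample size stand as written.

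**What to change.** 1. Bring the abstract and sections 3.1.1, 3.1.3.1 and 4.1 into line with 3.1.4, so that StimQ and ERPQ are completed at visit 1 **before allocation is revealed**. The order matters because both are parent-reported, and 3.1.3.1 and 4.1 now place assignment ahead of the questionnaires.
2. In 6.3, replace the three t-tests with one repeated-measures model of StimQ with terms for arm, visit, arm-by-visit, baseline StimQ and site.
3. Prespecify one lead StimQ contrast, either the final visit or the average over visits, at the sponsor's choice. Report the other visit-specific differences as descriptive.
4. If baseline StimQ is not to be collected, delete the baseline clause from 3.1.4 and still use the repeated-measures model with site.

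**Cost.** One model replaces three tests. Visit 1 takes longer for the parent, by an amount the documents do not allow one to estimate, since no completion times are given. Time may be tight under 8.4.1, which allows families to be approached and enrolled at the 6 month visit itself, before the child sees the provider.
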